#### **5.5 Packaging**

- There will be no comparative device for the OxyChip.
- The OxyChips will be sterilized in individual packaging, as described previously.
- Labels identifying the units as “Investigational Devices: Sterilized OxyChips” will be used on all storage containers.

#### **5.6 Receiving, Storage, Dispensing and Return**

##### **5.6.1 Receipt of study device**

The date of manufacture of the OxyChips by the EPR Center will be kept on an inventory, which will include the name of the technician manufacturing the device, and a device log filled out to track the devices. Any damaged or unusable study devices found at the time of the implantation procedure will be documented in the study files and on the inventory. Devices delivered to the operating room or procedure room will also be logged in the Sponsor’s inventory log.

##### **5.6.2 Storage**

The sterilized OxyChips will be stored in sterile packaging at room temperature (20°C to 23°C [68°F to 75°F]) and at a relative humidity range not to exceed 70%. All packaging materials will be examined regularly for defects and extraneous matter. If wet or damaged packages are observed, they will not be released. Access to the location where the OxyChips are stored will be limited (i.e. in a lock box or in a room with a lock). The OxyChips will be stored on a closed shelf in a room with a lock to limit access. The OxyChips will be stored away from any sprinkler heads, 18 inches away from the floor or ceiling and 2 inches away from the wall. The OxyChips will be positioned such that they do not get bent, crushed, punctured, or compressed.

##### **5.6.3 Dispensing of study device**

Regular device reconciliation checks will be performed. Information tracked will include which device was implanted in a given subject; which device containers were opened to select the specific device to be implanted in the subject; whether the subject actually received the assigned device; which devices were inadvertently damaged in handling/dispensing. This reconciliation will be logged on the device reconciliation form and signed and dated by the study team. After removal of the OxyChip from the pathology specimen, the OxyChip will be returned to the sponsor for recalibration and inspection.

##### **5.6.4 Return or destruction of study device**

At the completion of the study, there will be a final reconciliation of study devices manufactured, devices consumed, and devices remaining. This reconciliation will be logged on the device reconciliation form, signed and dated. Any discrepancies noted will be investigated, resolved, and documented prior to completion of the study. Devices destroyed on site will be documented in the study files.

## **6 Study Procedures**

### **6.1 Pre-enrollment (Phase 1A, 1B)**

1. Review of any prior imaging studies; this could include an MRI, CT scan or PET/CT scan.
2. Review of pathology to confirm tumor histology for Phase 1B
3. The study will be introduced to the patient and the IRB-approved consent form reviewed and signed if the patient agrees to participate. No study related procedures should be performed prior to informed consent being obtained.
4. Physical exam performed within 6 weeks of OxyChip implantation procedure. This may be performed by non-study physician or physician extender as standard of care or by study physician.
5. Pregnancy test or other standard proof of non-pregnancy for women of reproductive capability at the discretion of the physician.
6. All other eligibility criteria will be reviewed and recorded, e.g., age, no pacemaker.
  - a. If platelet blood count and/or absolute Neutrophil count (ANC) have not been drawn for standard of care within the last months prior to the implantation of the OxyChip, the patient will be given the option to have a venipuncture for research purposes only in order to confirm eligibility.

### **6.2 Placement of the OxyChip (Phase 1A, 1B)**

1. Placement of the OxyChip with a minimally invasive approach (see 5.2.1).

### **6.3 Post OxyChip implantation assessment (Phase 1A, 1B)**

1. Phase 1A patients will be evaluated at least monthly prior to OxyChip removal for assessment\* with respect to any adverse effects for the primary objective.
2. Phase 1B patients will be evaluated weekly during radiotherapy or prior to each chemotherapy administration or follow-up appointment for assessment\* of any adverse effects for the primary objective.

\* Assessments by non-study physicians or physician extenders as part of standard of care are acceptable. If a patient cannot or does not return for an evaluation, the study team will contact the patient by phone or email to assess for development of new adverse effects or changes in health status.

### **6.4 Oxygen measurements (Phase 1A, 1B)**

1. The area over the OxyChip is examined for signs of infection or inflammation at each session.
2. Non-invasive tumor oxygenation measurements are obtained.(see 5.2.2)
- 3.

### **6.5 Pre-operative assessment (Phase 1A, 1B)**

1. The area over the OxyChip is examined for signs of infection or inflammation. This assessment can be performed within two weeks prior to surgery depending on logistical constraints, or by the treating physician prior to surgery.
2. Physical exam is performed within two weeks of surgery. This may be performed by non-study physician or physician extender as standard of care or by study physician.

## 6.6 Removal of OxyChip (Phase 1A, 1B)

1. Surgical resection of the tumor with OxyChip removal in the specimen followed by pathology evaluation of specimen. (see 5.2.4 and 5.2.5)

## 6.7 Visits after removal of the OxyChip (Phase 1A, 1B)

1. Patients will be evaluated 1-2 weeks after surgical resection with removal of the OxyChip for evaluation of healing. This may be performed by a non-study physician as standard of care or by a study physician. If the patient cannot or does not return for post-operative evaluation, the study team will contact the patient by phone or email to check for development of new adverse events or changes in health status.
2. While we do not expect any long-term effects following removal of the OxyChip, we will collect and examine results from laboratory tests and physical exams obtained *ad hoc* as a part of routine follow-up up to 12 months following implantation.

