## Study Summary

Title	A Single-Institutional, Phase I Trial of Repeated Oxygen Measurements in Subcutaneous Tumors by Electron Paramagnetic Resonance (EPR) Oximetry using an Implantable Oxygen Sensor (OxyChip)
Short Title	EPR Oximetry using OxyChip
Protocol Number	D14007, CPHS 28499
Phase	First-in-humans, early feasibility study for OxyChip implantation with subsequent expansion to a larger Phase I trial. Phases: 1A (tumor with planned surgical resection only and consequently with an expected duration of implantation for up to 4 weeks); and 1B (tumor with neoadjuvant radiation therapy or chemotherapy followed by planned surgical resection, with expected duration of implantation of up to 12 weeks for radiation and 24 weeks or more for chemotherapy.) OxyChip implant duration for both phases can be extended to 52 weeks excluding the first 6 patients enrolled into Phase 1A where implant duration is up to 4 weeks.
Methodology	Phase I (first-in-human, early feasibility trial)
Study Duration	5 years
Study Center(s)	Single institution: Dartmouth-Hitchcock Medical Center (DHMC)
Objectives	Primary: Establishment of safety of OxyChip implantation in humans; Secondary: establishment of feasibility of OxyChip for measurements of oxygen using EPR oximetry in humans.
Number of Subjects	60 total evaluable subjects planned: 3 subjects in Phase1A will be evaluated and reviewed before enrolling another 3 subjects. After completion of the first 6 subjects in Phase 1A, if there are no unacceptable toxicities from the OxyChip, that cohort will be expanded to a total of 30 subjects. Phase 1B will consist of one cohort of 3 subjects receiving chemotherapy and one cohort of 3 subjects receiving radiotherapy. Once a cohort has enrolled 3 subjects and there are no unacceptable toxicities from the OxyChip, the completed cohort will be expanded to enroll additional subjects. No more than 30 subjects will be enrolled in Phase 1B. Phase 1A and Phase 1B will be evaluated separately with regards to this expansion; i.e. , Phase 1A may expand to 30 subjects while Phase 1B is still accruing.
Diagnosis and Main Inclusion Criteria	Tumors, located within 3 cm of skin or mucosal surface AND tumor resection is planned.

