### 1.5.5 Compliance with FDA and Dartmouth IRB regulation

[figure not shown]
We have obtained approval from the FDA (Investigational Device Exemption) and the Dartmouth IRB (CPHS) to increase the total number of enrollments from the initial cohort of 12 to 60 patients, and to extend

the length of OxyChip residence in the tumor for up to 1 year. Currently, we have completed the Phase 1 safety and efficacy study requirement set by the

to 1 year. Currently, we have completed the Phase 1 safety and efficacy study requirement set by the FDA.

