## 3 Study Design

### 3.1 General Design

This is a Phase 1 clinical trial. Total enrollment will be 60 evaluable patients. Evaluable patients will be defined as patients who have the OxyChip implantation for the minimum of 3 days.

The study is split into Phase 1A (shorter duration of implantation with no other cancer therapy planned prior to excision) and Phase 1B (longer duration of implantation that is typically up to 12 weeks while receiving radiation therapy or longer if receiving neoadjuvant chemotherapy prior to surgical excision), as described below. OxyChip implant duration for both phases can be extended to 52 weeks (excluding the initial 6 evaluable patients in Phase 1A which may have the OxyChip implanted up to 4 weeks).

[figure not shown]
The initial 6 evaluable patients in Phase 1A will have the OxyChip placed for a short duration (up to 4 weeks) after which the OxyChip will be removed when the tumor mass is resected, prior to delivery of any further therapies. After successful implantation and removal of the OxyChip without any unacceptable toxicity in the first 6 evaluable patients, the Phase 1A cohort will be expanded to a total of 30 patients. In order to complete the safety and toxicity assessment of the short-term implantations, we will require that at least 3 patients have OxyChip implantations for a duration of at least 2 weeks, prior to proceeding to Phase 1B (long term implantation). This may require enrollment of additional patients in Phase 1A in order to meet this criterion. Phase 1B will consist of one cohort of 3 evaluable patients receiving chemotherapy treatment and one cohort of 3 evaluable patients receiving radiotherapy. Only after a full evaluation of the first 3 patients that underwent chemotherapy will additional patients receiving chemotherapy be enrolled. Similarly, only after a full evaluation of the first 3 patients that underwent radiotherapy will additional patients receiving radiotherapy be enrolled. The two cohorts of 3 patients in Phase 1B are independent of each other, so either of these cohorts may continue accrual after the initial 3 patients while the other is still accruing for the initial 3 patients. A total of 30 patients will be enrolled in Phase 1B. .

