#### 5.2.4 OxyChip and Fiducial removal

The OxyChip and fiducial(s) will be excised with the surgical specimen. The surgeon determines the timing of surgery, but it will typically be planned to be within 4 weeks for Phase 1A, or after completion of radiotherapy or chemotherapy for Phase 1B, although the OxyChip may remain implanted for up to 52 weeks for both Phases (excluding the first 6 patients enrolled into Phase 1A). The minimum time from implantation to surgical excision required for inclusion is 3 days. Note, patients in Phase 1B are expected to have the OxyChip in place for a minimum of 5 weeks (the expected duration of radiation therapy). The protocol and goals for removal will be as follows:

- (i) All attempts will be made to maintain the OxyChip in the tissue specimen, without disrupting the shape or position within the tumor mass.
- (ii) In collaboration with the surgeon, after the patient has been anesthetized, imaging of the fiducial(s) will occur prior to surgery in order to identify the putative location of the OxyChip and facilitate surgical removal.
  - a. We anticipate the fluoroscopy will be sufficient for identification of the fiducial prior to surgical removal (and after). However, due to concerns that more advanced imaging may be necessary, the first three patients with fiducial implantation will have their surgery performed at DHMC in the Center for Surgical Innovation (CSI). If fluoroscopy is sufficient for identification, then subsequent surgeries can be performed in standard operating rooms as desired if fluoroscopy is available for identification of fiducials before and after surgery.
    - i. In the first three patients in the CSI, if the fiducial is not found prior to surgery either CT or MRI imaging will be performed to identify the fiducials. If the fiducials are found within the expected surgical field, or reasonably adjacent, fiducials will be removed during surgery. If the fiducials are found in an unanticipated area, consultation between the PI and the surgeon will occur as to whether surgical resection is acceptable. All decisions regarding surgery will be at the discretion of the surgeon. If no fiducials are found after advanced imaging prior to surgery, then surgery will proceed as planned as all reasonable measures will have been taken to identify the location of the OxyChip at that time.

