  - b. After surgical resection, fluoroscopy will be performed on the specimen prior to surgical closure in order to ensure that the fiducials have been removed. If the fiducials are present in the specimen, it is highly likely that the OxyChip has been removed and surgical closure will occur. If the fiducials are not found then advanced imaging via CT or MRI will occur to attempt to identify the fiducials in the patient. If the fiducials are then identified, in consultation with the surgeon, that area will be removed if it is deemed acceptably close to the surgical field. If the fiducial is not visualized, a discussion will be had with the surgeon regarding further excisions of margins, as well as a search of the surgical field for an

OxyChip/fiducial that may have fallen out at the time of surgery. In this circumstance, all attempts will be reasonably made to ensure removal of the OxyChip, but the surgeon will have discretion about what is clinically appropriate.

If a definitive surgery is deemed unnecessary after chemotherapy therapy or radiotherapy (Phase 1B), or if a definitive surgery is delayed beyond the expected time point (> 52 weeks) due to unforeseen circumstances, the OxyChip may be removed in a minor procedure under local anesthesia. The OxyChip will be identified using the fiducials as surrogates via ultrasound or fluoroscopy, and that area will be excised using similar considerations noted above. This procedure will be performed at the first available time deemed safe for the patient as determined by the primary oncology team.

In the circumstance where a patient dies prior to surgery and the OxyChip is still in place, a discussion will be had with the next of kin regarding removal of the OxyChip prior to burial. If next of kin agrees to allow OxyChip removal, it may be removed via a small surgical procedure.

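### Section 6.7(2) looks for late effects after OxyChip removal but counts its 12 months from implantation, so the post-removal window shrinks as residence lengthens, to 1 day at the permitted 52 weeks

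*Combined protocol and SAP*

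**What the plan says.** Section 6.7 covers the period after the chip has been taken out. Item 1 sets a healing check 1 to 2 weeks after resection. Item 2 says that no late effects of the chip are expected after removal, but that laboratory and examination results obtained "as a part of routine follow-up up to 12 months following implantation" will be collected and examined. The clock in item 2 therefore starts when the chip goes in.

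On residence, section 3.1 states: "OxyChip implant duration for both phases can be extended to 52 weeks (excluding the initial 6 evaluable patients in Phase 1A" (those six are limited to 4 weeks). Section 5.2.4 repeats the allowance: "although the OxyChip may remain implanted for up to 52 weeks for both Phases". Section 1.5.5 describes the approved extension as "the length of OxyChip residence in the tumor for up to 1 year", which is the same length as the item 2 window. Section 5.2.4 also makes provision "if a definitive surgery is delayed beyond the expected time point (> 52 weeks) due to unforeseen circumstances". For Phase 1B, the Study Summary gives an "expected duration of implantation of up to 12 weeks for radiation and 24 weeks or more for chemotherapy".

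Survival follow-up in section 4.4.2 also runs for a year from implantation. Exclusion criterion 6 in section 4.2 mentions a year of follow-up in a sentence about the period after removal, but does not say when that year begins.

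**The concern.** Item 2 states a post-removal purpose but uses a clock that can run out on the day of removal. The longer the chip stays in, the less of the 12 months is left afterwards, so the patients with the greatest exposure get the shortest look after removal.

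This is the first use of LiNc-BuO in humans (section 1.2), and section 1.7 accepts that its risk in humans is unknown. The 52-week allowance rests on rat data and on up to 32 days of residence in the first six patients (section 1.6.2). The longest human residence reported is 141 days (section 1.7). Patients beyond that have the least human precedent.

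What lapses is the study's own review of routine results. After the healing check, it is the only route apart from survival follow-up by which the study looks for a new late effect rather than waiting for a report. Section 8.2 has subjects questioned at study visits, and the last visit listed in section 6 is the healing check.

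**Working it through.** **Inputs**
- End of item 2 collection: 12 months from implantation (6.7), taken as 365 days.
- Maximum residence: 52 weeks = 52 × 7 = 364 days (3.1, 5.2.4).
- Limit for the first six Phase 1A patients, and typical timing for the rest of Phase 1A: 4 weeks = 28 days (3.1, 5.2.4).
- Expected Phase 1B residence: at least 5 weeks = 35 days (5.2.4); up to 12 weeks = 84 days for radiotherapy; 24 weeks = 168 days or more for chemotherapy (Study Summary).
- Longest residence reported: 141 days (1.7).

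The plan states no length for the post-removal window, so there is no figure of its own to reproduce.

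**Formula:** days of collection after removal = 365 − residence in days.

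| Residence | Calculation | Days left after removal |
|---|---|---|
| 4 weeks | 365 − 28 | 337 |
| 5 weeks | 365 − 35 | 330 |
| 12 weeks | 365 − 84 | 281 |
| 141 days | 365 − 141 | 224 |
| 24 weeks | 365 − 168 | 197 |
| 36 weeks (illustration) | 365 − 252 | 113 |
| 48 weeks (illustration) | 365 − 336 | 29 |
| 52 weeks | 365 − 364 | 1 |

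If the year spans a leap day, each entry rises by one, so the last becomes 2. Removal on day 365 leaves nothing, and after a later removal the window has closed before the chip is out.

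**Against the healing check.** The check falls 7 to 14 days after resection. Its later edge passes the item 2 cutoff once residence exceeds 365 − 14 = 351 days (about 50.1 weeks), and its earlier edge once residence exceeds 365 − 7 = 358 days (about 51.1 weeks). The check still takes place, because it is counted from resection, but beyond 358 days no item 2 collection follows it.

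**The case against.** The strongest reply is that implantation is a reasonable anchor. Exposure starts there, survival uses the same date, every patient gets the same 12 months, and the end date is defined even if the chip is never removed. Patients with long residence are not observed less overall. More of their year is covered by evaluation while the chip is in place: at least monthly in Phase 1A, and weekly during radiotherapy or before each chemotherapy administration in Phase 1B (3.1, 6.3). Tissue is examined at removal (5.2.5).

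The 1-day figure is also the extreme case, and no document reports a patient near 52 weeks. What lapses is modest, since item 2 schedules no test or contact and depends on whatever routine care produces. Device-related effects that are observed or volunteered remain recordable and reportable with no calendar limit, and those identified are followed until they resolve or stabilize (8.3.1.1, 8.3.1.4, 8.3.2). The primary endpoint (3.2) is not defined by this window, and the cohort decisions wait until more than 2 weeks after removal (3.1).

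Most of this stands, and it limits the weight of the point. It does not remove it. An implantation anchor suits survival, but it does not serve a stated interest in what happens after removal. Evaluation during residence and histology at removal inform on exposure, not on later effects. Open-ended reporting depends on someone noticing an effect and raising it. If few patients reach long residence, they are still the only human evidence on removal after long exposure.

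**Conclusion.** The concern holds: applied exactly, item 2 can defeat its own purpose, and no other section gives it a removal anchor. At the stated typical or expected residences of 4 to 24 weeks, 197 to 337 days remain, which is ample. The window then narrows to 1 day at the permitted maximum and is gone for later removal.

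The arithmetic is certain, given a 365-day year. How much it matters depends on how many patients have long residence, which the documents do not give; chemotherapy residence is open-ended above 24 weeks. The first six Phase 1A patients, limited to 4 weeks, are not affected. This should be corrected, but it does not threaten the primary endpoint or the decisions to expand cohorts.

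**What to change.** **Preferred change.** Keep the 12-month limit in 6.7(2) and add a minimum period after removal, so that collection ends at the later of the two. The sponsor should set the length, M days; the documents do not dictate one. Added time per patient is max(0, residence + M − 365):
- M = 90 (illustrative): nothing is added up to 365 − 90 = 275 days of residence (39.3 weeks); at 52 weeks, 364 + 90 − 365 = 89 days.
- M = 180 (illustrative): nothing is added up to 365 − 180 = 185 days (26.4 weeks); at 52 weeks, 364 + 180 − 365 = 179 days.
- Any M up to 365 − 168 = 197 adds nothing at 24 weeks or less.

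**Alternative.** Count the full 12 months from removal. This adds the residence time for every patient: 28 days at 4 weeks, 84 at 12, 168 at 24 and 364 at 52. It would also need a defined end date for a patient whose chip is never removed. Section 5.2.4 leaves that possible: "all attempts will be reasonably made to ensure removal of the OxyChip, but the surgeon will have discretion about what is clinically appropriate". The present limit already supplies such a date, so this addition is needed only under re-anchoring.

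**Under either option,** report residence time and post-removal observation time beside any statement on late effects, and state when the year mentioned in section 4.2 begins. The survival anchor in 4.4.2 can stay.

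**Cost.** More review of routine records and a later last-patient date; no new visits or procedures. The Study Summary gives a 5-year duration, and section 11.1 gives a grant end of 06/30/2020, which is 264 days after the version 8 date of 10/10/19. These dates weigh far more on full re-anchoring than on a minimum period. Whether other funding exists is not stated. The consent pages were not available, so whether they need a matching change could not be checked.
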